4.7.1.3 Reporting of serious adverse events

All SAEs have to be reported, whether or not considered causally related to the investigational product or to the study procedure(s). All SAEs will be recorded in the eCRF.

Investigators and other site personnel must inform appropriate AstraZeneca representatives of any SAE that occurs in the course of the study within 1 day (ie, immediately but not later than the end of the next business day) of when he or she becomes aware of it.

SAE information will be entered and submitted into the Web Based Data Capture (WBDC) system on the relevant eCRF modules. An automated email alert will be sent to the designated AstraZeneca representative who will work with the Investigator to ensure that all the necessary information is available in the system within the required time frames, but taking advantage of the time allocated in those timelines. The AstraZeneca representative will notify the appropriate AstraZeneca Drug Safety department through the WBDC system via email that a completed electronic SAE module and relevant information from other appropriate eCRF modules is available in the WBDC system. If the system is unavailable, the Investigator should fax a paper back-up SAE report to the AstraZeneca representative immediately, recognising that the same reporting time frames still apply. The Investigator is responsible for completing the eCRF as soon as the system becomes available again.

The AstraZeneca representative will work with the Investigator to compile all necessary information and ensure that the appropriate Safety Database Data Entry Site receives a report within the required timeframes, which will be detailed in a study specific Safety Plan. The Investigator must report follow-up information on SAEs within the same time frames. If a non-serious AE becomes serious, this and other relevant follow-up information must also be provided to AstraZeneca within the time lines described above.

The Investigator and/or Sponsor are responsible for informing the Ethics Committee and/or the Regulatory Authority of the SAE, as per local requirement. For studies in countries implementing the EU Clinical Trials Directive, this will be taken care of by AstraZeneca or their representative (see Section 8.1).

4.7.2 Laboratory safety measurements and variables

4.7.2.1 Methods of assessment

Clinical chemistry testing will be performed at Visits 1, 3, 5 and 7 (Weeks -6, 0, 6 and 12) and will include: albumin, total bilirubin, blood urea nitrogen, CK, serum creatinine, ALT (SGPT), aspartate aminotransferase (AST) (serum glutamic oxaloacetic transaminase

(SGOT)), fasting glucose, alkaline phosphatase, calcium, phosphate, potassium, sodium, total protein and gamma-glutamyl transferase (GGT). At Visits 2, 4 and 6 (Weeks -2, 4 and 10) abbreviated clinical chemistry tests will be performed, consisting of: CK, serum creatinine, ALT, AST and TSH (TSH only at Visit 2 (Week -2)).

Haematology testing will be performed at Visits 1, 3, 5 and 7 (Weeks -6, 0, 6 and 12), which will include: platelet count, haemoglobin, haematocrit, red blood cell (RBC) count, RBC indices (mean cell volume (MCV), mean cell haemoglobin (MCH), mean cell haemoglobin concentration (MCHC)), white blood cell (WBC) count, WBC differential (neutrophils, bands, lymphocytes, monocytes, eosinophils, basophils).

A 10 mL mid-stream urine sample will be collected at Visits 3, 4, 5, 6 and 7 (Weeks 0, 4, 6, 10 and 12) for analysis at the central laboratory. For Visits 3, 5 and 7 (Weeks 0, 6 and 12), urinalysis sample is to consist of: visual description (colour and appearance), a dipstick test (specific gravity, pH, protein (qualitative), glucose, ketones, bilirubin and blood), microscopy (RBC, WBC, bacteria, casts and crystals). For Visits 4 and 6 (Weeks 4 and 10), the following abbreviated urinalysis is to be performed: a dipstick test (specific gravity (if suspected/necessary), protein (qualitative) and blood). At Visits 4 to 7 (Weeks 4 to 12), for any patients with dipstick protein ++ or greater where this represents $a \ge 1$ grade shift (eg, from + to ++ or trace to ++) from the baseline visit, the central laboratory will automatically perform a quantitative assessment of total protein, albumin and creatinine.

If the urine protein/creatinine ratio is >0.5 mg protein per mg creatinine (US) or >56 mg protein per µmol creatinine (RoW), the Investigator may stop study medication following consultation with the relevant AstraZeneca personnel (eg, Clinical Study Team Physician).

An assay of serum β -HCG concentration will be performed for women of childbearing potential at Visit 1 (Week -6). If the test is positive for pregnancy, the patient should not enter the study. An assay of serum β -HCG concentration will be performed at all subsequent visits if it is suspected that the patient may have become pregnant. If the test is positive for pregnancy the patient will be withdrawn from the study. Assays of serum β -HCG will be performed on blood samples drawn for the clinical chemistry/abbreviated clinical chemistry testing.

Vital signs (sitting blood pressure (BP) and pulse rate (PR)) will be assessed at Visit 1 (Week -6) and Visit 7 (Week 12).

In the event of elevated liver function tests, see Appendix C for guidance with regards to management of elevated liver enzymes.

In the case of new or increased symptoms of muscle pain/myopathy/elevation of CK to >5x ULN developing after randomisation, see Appendix D for guidance with regards to management of increased CK.

In the event that serum creatinine levels increase >30% from the baseline value, see Appendix E for guidance with regards to elevated serum creatinine.

Additional testing required (unscheduled visits) due to elevated values and/or symptoms (liver enzymes, CK, serum creatinine, see Appendix C, D and E) will be performed at the central laboratory.

Other laboratory tests which are performed outside the CSP will not be analysed by the central laboratory.

4.8 Volume of blood sampling and handling of biological samples

The total volume of blood that will be drawn from each patient in this study is as follows:

Assessment		Sample volume (mL)	No. of samples	Total volume (mL)
Pharmacodynamic	(Lipid assay including TC, LDL-C, HDL-C, TG, nonHDL-C, LDL-C/HDL-C, TC/HDL-C, nonHDL-C/HDL-C, ApoB, ApoA-I, hs-CRP)	5	14	70
Exploratory	Biomarkers: Refer to Section 2.3; Exploratory objective	5	10	50
Safety	Clinical chemistry	3.5	4	14
	Abbreviated clinical chemistry	3.5	3	10.5
	Haematology	3	4	12
Total				156.5

Table 5Volume of blood to be drawn from each patient

Note: For patients consenting to the genetic study (Appendix K) an additional 9 - 10 mL will be taken. It should also be noted that additional samples may be required following safety findings (refer to Appendices C, D and E).

Clinical Study Protocol Drug Substance Rosuvastatin Study Code D356FC00003 Date

4.8.1 Analysis of biological samples

The analyte stability limits defined by the central laboratory will be applied to all analyses performed on behalf of AstraZeneca. The central laboratory will not analyse samples that fall outside these stability limits. Analytical data will not be reported if found to have been derived from a sample that fell outside these stability limits. The standards of procedure followed by the central laboratory may be amended in accordance with its Standard Operating Procedures (SOPS). The central laboratory will inform AstraZeneca of the stability limits relevant to this study before the first patient gives informed consent to take part in the study.

If the central laboratory chooses to sub-contract the analytical work to another laboratory, the central laboratory must assure itself and provide assurance to AstraZeneca that the other laboratory will apply defined stability limits to all analyses performed on behalf of AstraZeneca. Samples falling outside these limits must not be analysed or data reported. The other laboratory will inform AstraZeneca of the stability limits relevant to this study before the first patient gives informed consent to take part in the study.

The central laboratory will provide the investigational sites with all the appropriate materials for specimen collection and sample processing, packaging, and shipping to the central laboratory. An Investigator laboratory manual providing detailed instructions will be provided to each investigational site before the study starts. A tourniquet may be applied, but for no longer than 2 minutes. Full details of sampling, sample preparation, and storage methods to be used are given in the Investigator laboratory manual.

Samples which will be analysed by the central laboratory will be labelled according to the guidelines provided by the central laboratory.

Shipment of samples to the central laboratory will be carried out according to the guidelines provided by the central laboratory. The samples are shipped the day of collection by express courier to ensure receipt at the central laboratory within the period of sample integrity (within 48 hours of blood drawing). The appropriate documentation should accompany the samples.

Analyses of samples from all clinic visits will be carried out as described in the central laboratory methodology manual, a copy of which will be distributed to each centre before any patient is enrolled.

4.9 Genetic measurements and co-variables

4.9.1 Collection of samples for genetic research

Full details of the optional generic research component to this study, including rationale, areas of interest and logistical information are provided in Appendix K.

5. DATA MANAGEMENT

Data will be entered in the WBDC system at the study site. Trained study personnel will be responsible for entering data on the observations, tests and assessments specified in the protocol into the WBDC system and according to the eCRF Instructions. The eCRF Instructions will also provide the study site with data entry instructions. Data entered in the WBDC system will be immediately saved to a central database and changes tracked to provide an audit trail. When data have been entered, reviewed, edited and Source Data Verification (SDV) performed the Principal Investigator will be notified to sign the eCRF electronically as per the agreed project process and data will be locked to prevent further editing. A copy of the eCRF will be archived at the study site.

Data collected from the completed eCRFs and laboratory data will be received electronically by an AstraZeneca representative. The processes will be documented in the Data Management Plan and the validation performed under the direction of the responsible Data Manager, according to the Data Validation Manual.

5.1 **Reporting of genotypic results**

Results from any genetic research performed will be reported separately from the CSR. AstraZeneca will not provide individual genotype results to patients, their family members, any insurance company, an employer, clinical study investigator, general physician or any other third party, unless required to do so by law. The patient's DNA will not be used for any purpose other than those described in the study protocol.

Individual patients will not be identified in any report or publication resulting from this work. The data and results of this study may be reviewed with collaborators and published, but neither the patient's name nor any other personal identifiers will appear in any publication or report.

6. STATISTICAL METHODS AND DETERMINATION OF SAMPLE SIZE

6.1 Statistical evaluation – general aspects

A comprehensive statistical analysis plan (SAP) will be prepared before unblinding of the data, and before database lock.

Experience in previous studies indicates that within-patient fluctuations in LDL-C exhibit autocorrelations lasting a period of several weeks. Thus, overall precision will be increased by using an average of 2 measurements taken at least 2 weeks apart. Since the onset of lipid-lowering treatments is largely complete by 4 weeks, an average of measurements made at 4 and 6 weeks will provide an accurate estimate of the treatment effect throughout this period. In this study, all baseline and on-treatment effects are assessed as the mean of 2

consecutive measurements made 2 weeks apart. For reporting purposes, the average of weeks 4 and 6 is termed the effect after 6 weeks of treatment.

Two-sided tests of statistical significance will be used throughout.

6.2 Description of outcome variables in relation to objectives and hypotheses

Primary outcome variable:

- Percentage LDL-C change from baseline to 6 weeks (mean of weeks 4 and 6) of combination therapy
- Statistical significance of the following 3 comparisons will be tested simultaneously by a Hochberg procedure to control for multiple comparisons:
 - 1. Rosuvastatin 20 mg + ezetimibe 10mg vs simvastatin 40 mg+ 10 mg ezetimibe
 - 2. Rosuvastatin 10 mg + ezetimibe 10mg vs simvastatin 40 mg+ 10 mg ezetimibe
 - 3. Rosuvastatin 20 mg + ezetimibe 10mg vs simvastatin 80 mg+ 10 mg ezetimibe

Secondary outcome variables:

The secondary outcome variables include:

- LDL-C, HDL-C, TC, TG, nonHDL-C, ApoB, ApoA-I, TC/HDL-C, LDL-C/HDL-C, nonHDL-C/HDL-C and ApoB/ApoA-I, hs-CRP; and the corresponding measures of effects are the respective changes from baseline
- Therapeutic lipid goals as described in American and European guidelines, with the corresponding measures of effect being the proportions of patients achieving goal

Exploratory

• Change in biomarkers (sitosterol, lanosterol, C4 and LpPLA2). An additional sample will also be drawn for possible other biomarkers and lipid fractions that are related to atherosclerosis

Clinical Study Protocol Drug Substance Rosuvastatin Study Code D356FC00003 Date

Safety

- AEs
- Vital signs (blood pressure and pulse rate)
- Clinical chemistry
- Haematology
- Urinalysis

6.3 Description of analysis sets

Efficacy analyses will be performed on intent-to-treat (ITT) last observation carried forward (LOCF), completers only and observed data. Per-protocol (PP) data will be available for subsequent analysis if required, though this is not anticipated.

The ITT population will consist of patients who have baseline and at least 1 post-baseline measurement.

LOCF will be interpreted as follows:

- If no data are available for a particular variable following commencement of therapy, then for that variable, the patient is not included in the ITT analysis
- If a measurement is not available for either Visit 4 or 5 (after 4 and 6 weeks of monotherapy, respectively), then the LOCF for the monotherapy phase will be determined as the last of the on-monotherapy measurements
- If a measurement is not available for either Visit 6 or Visit 7 (after 4 and 6 weeks of combination therapy, respectively), then the LOCF for combination therapy will be determined as the last of the on-combination therapy measurements
- In the case where there are no measurements available in the combination therapy phase, then the monotherapy LOCF will be carried forwards to impute the combination therapy LOCF

Completers are the patients in the ITT population who have had at least 1 measurement made following combination therapy. An analysis of completers will be done specifically to show combination treatment efficacy in the absence of dilution of effect, due to carryover of LOCF data from the monotherapy phase.

Patients will be evaluated using randomised treatment.

There will be 2 safety populations. The dietary lead-in safety population will consist of all patients who entered the dietary lead-in period. The randomised safety population will consist

of all patients who were randomised and took at least 1 dose of study medication. Patients in this safety population will be analysed by treatments and doses actually received as follows:

Period	Treatments
Dietary lead-in	Diet
Randomised (0 to 12 weeks)	Rosuvastatin or simvastatin monotherapy followed by combination therapy of rosuvastatin or simvastatin with ezetimibe

Table 6Safety populations

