6.4 Method of statistical analysis

The primary analysis will be made on LDL-C as the LOCF in the ITT population. A supportive analysis will be made on the completer ITT population.

Lipids and lipoproteins (as part of the secondary objectives) are: TC, LDL-C, HDL-C, TG, ApoA-I, ApoB, nonHDL-C, ApoB/ApoA-I, TC/HDL-C, LDL-C/HDL-C, nonHDL-C/HDL-C and hs-CRP. Baseline for calculating percentage change in a lipid or lipoprotein will be the mean of values from Visits 2 and 3 (Weeks -2 and 0). Monotherapy will be assessed as the mean of Visits 4 and 5 (Weeks 4 and 6), and combination therapy will be assessed as the mean of Visits 6 and 7 (Weeks 10 and 12).

The effect of combination therapy will be assessed by analysis of co-variance (ANCOVA) using geometric percentage change, where the response variable is the logarithm of the ratio of the treatment value divided by the corresponding baseline value, and treatment and centre are the explanatory variables. Estimates of treatment effect, and their 95% CI, will be exponentiated to produce estimates of percentage change. For comparison with other studies, point estimates and confidence intervals will also be calculated arithmetically on the percentage change from baseline. However, the p-values for specified comparisons will be calculated for the geometric analysis only.

The estimates of the additional effects on lipids and lipoproteins of adding ezetimibe 10 mg to rosuvastatin 10 mg or 20 mg will be calculated in the same way using the geometric mean of the 2 monotherapy visits as baseline. Corresponding 95% CIs will be computed.

Depending on the distribution of patients across centres, it may be sensible to pool some small centres together by region. This will be discussed and agreed by biostatistical personnel and the clinical team at AstraZeneca before database lock.

The numbers and percentages of patients reaching appropriate goals will be summarised. Since the prescribed goals may change over time, the goals used in the evaluation will represent the current regional guidelines for this patient population at the time when the SAP is finalised (prior to database lock).

Formal analysis will be by logistic regression with terms for baseline LDL-C, centre and treatment in the model. Hypothesis testing in logistic regression models will be performed using likelihood ratio tests.

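### The primary LOCF rule enters statin-only LDL-C as the combination-therapy result, which biases the primary contrasts if the share of such patients differs by arm

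*Protocol*

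**What the plan says.** The primary variable in Section 6.2 is "Percentage LDL-C change from baseline to 6 weeks (mean of weeks 4 and 6) of combination therapy", that is, the mean of Visits 6 and 7. Section 6.4 states: "The primary analysis will be made on LDL-C as the LOCF in the ITT population". Section 6.3 defines the set: "The ITT population will consist of patients who have baseline and at least 1 post-baseline measurement". A patient with a Visit 4 or 5 value and nothing later therefore belongs to the primary analysis, and for that patient "then the monotherapy LOCF will be carried forwards to impute the combination therapy LOCF".

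The protocol sees the consequence. Section 6.3 plans a completer analysis to show efficacy "in the absence of dilution of effect, due to carryover of LOCF data from the monotherapy phase", and also lists an observed-data analysis. Section 6.4 ranks the former: "A supportive analysis will be made on the completer ITT population". Section 6.3.1 summarises withdrawals by visit, reason and treatment group.

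For the added effect of ezetimibe (secondary objective 7), Section 6.4 describes the same calculation "using the geometric mean of the 2 monotherapy visits as baseline". It does not say which data set that estimate uses.

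**The concern.** The endpoint is the response to statin plus ezetimibe. For the affected patients the analysed number is the response to statin alone, so their added ezetimibe effect is zero by construction. In a between-arm comparison, the arm with more such patients looks worse by an amount that reflects when patients left, not how well the combination lowers LDL-C.

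Unequal shares are possible. Treatment is open-label (Section 3.6.1), the primary contrasts compare different statins and doses, and Section 3.2.2 notes that statins are usually started lower than some patients here will start. The documents do not show that the shares will differ, or in which direction. The concern is that the primary analysis has no protection if they do.

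**Working it through.** **Inputs.** Planned difference 5 points, SD 13, 177 ITT patients per arm, about 95% power per contrast, 10% dropout after randomisation, and an approximately uniform ezetimibe effect across statins (all Section 6.5). Ezetimibe effect e: 13 points on rosuvastatin 40 mg, and about 15%, read here as percentage points (both Section 1.1). Assumed: two-sided alpha 0.05, since no number is given, and every arm-specific share below.

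**Step 1: the protocol's own figure.** n = 2(1.960 + 1.645)² × (13/5)² = 175.7, so 176 per arm. The noncentral-t version gives 177 (power 0.9504, against 0.9493 at 176). The stated 177 reproduces.

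**Step 2: bias.** Let dR and dS be the shares of the rosuvastatin and simvastatin arms with monotherapy values only. Each arm's mean reduction is diluted by e × d, so

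apparent difference = true difference − e × (dR − dS).

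For a 5-percentage-point gap: 0.05 × 13 = 0.65 and 0.05 × 15 = 0.75 points, or 13% and 15% of 5.

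**Step 3: operating characteristics** with e = 15, arm variance 13² + d(1 − d)e², n = 177 per arm, normal approximation. The last column is the two-sided rejection rate when the true difference is zero.

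| dR | dS | Apparent difference (true 5) | Power | Rejection rate, true 0 |
|---|---|---|---|---|
| 0 | 0 | 5.00 | 0.951 | 0.050 |
| 10% | 10% | 5.00 | 0.928 | 0.050 |
| 7.5% | 2.5% | 4.25 | 0.847 | 0.082 |
| 10% | 5% | 4.25 | 0.837 | 0.081 |
| 5% | 10% | 5.75 | 0.978 | 0.081 |
| 10% | 0 | 3.50 | 0.692 | 0.184 |
| 0 | 10% | 6.50 | 0.995 | 0.184 |

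With e = 13, a 5-point gap gives 4.35 or 5.65 and a rejection rate of about 0.074 to 0.075. Counting the shift alone, without the added variance, power at 4.25 is Φ(4.25/(13 × √(2/177)) − 1.96) = Φ(1.115) = 0.87. These figures take the SD of 13 as not already including the imputed mixture.

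**Step 4: the scale of the p-values.** Section 6.4 takes p-values from the log-ratio analysis only. From the rosuvastatin 40 mg figures (70% total reduction, 13 points of it from ezetimibe), residual LDL-C goes from 43% to 30%: ln(30/43) = −0.360. A 5-point gap shifts the contrast by 0.05 × 0.360 = 0.018. Against a comparator 5 points worse, ln(35/30) = 0.154, this is about 12%. Assumed monotherapy/combination reductions of 40/55, 45/60 and 57/70%, with the better arm 5 points lower still, give 12.2%, 11.9% and 9.9%.

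**Step 5: objective 7, if it uses LOCF data.** The undiluted increment is 1 − exp(−0.360) = 30.2%. With 5% carried forward it reads 1 − exp(−0.95 × 0.360) = 29.0%; with 10%, 1 − exp(−0.90 × 0.360) = 27.7%. No imbalance between arms is needed.

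**Step 6: how large a gap is credible.** The rule reaches only patients with a Visit 4 or 5 value and no Visit 6 or 7 value. If dropout were even over 12 weeks (an assumption), about 6/12 of the 10%, roughly 5%, falls between Weeks 4 and 10. A 5-point gap then means something like 7.5% against 2.5%. The 10% against 0 rows are extremes.

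**The case against.** The strongest reply is that the dilution is disclosed and answered. Completer and observed-data analyses are planned, withdrawals are tabulated by arm, and only the label of primary is in dispute. That lowers the severity. It does not remove the point: the primary p-values come from the affected analysis, and completers are selected after randomisation, so they do not restore the randomised comparison.

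A second reply is about the target of estimation. Section 3.2.1 says that patients are randomised once, to a treatment sequence. Not reaching ezetimibe is then an outcome of that sequence, and giving no credit for it is a recognised convention. This has some force. But the carried value is an earlier on-statin measurement, not the patient's LDL-C at Weeks 10 to 12, so it does not measure the result of the sequence either.

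Third, unequal dropout is unproven. Section 3.2.2 says that high-dose initiation has generally been well tolerated, site staff do not see lipid results, and Section 3.3.5.2 asks that discontinued patients be followed on schedule where possible. The rosuvastatin 40 mg figures also belong to no arm of this trial. This stands, which is why the sizes are conditional.

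Two further inferences are tempting and unsupported. A reader might infer that carrying values forward understates uncertainty here. That is not shown: in Step 3 the imputed mixture adds variance. A reader might also infer that objective 7 is certainly affected. The protocol does not name its data set, so that part is conditional.

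**Conclusion.** The concern holds in a bounded form. The stated primary analysis treats statin-only values as combination results, and its contrasts are biased whenever the monotherapy-only shares differ between arms. The bias can run either way, so LOCF cannot be called conservative.

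The size depends on shares that the protocol does not give. With equal shares and a uniform ezetimibe effect the contrast is unbiased, so the documents do not support reading the primary result as biased in every case. A 5-point gap costs or adds roughly 10-15% of the planned difference across the two scales. Objective 7 would be biased towards no effect, modestly, if LOCF data are used for it.

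This is worth changing before the analysis is fixed. It does not invalidate the design or the sample size.

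**What to change.** Make the primary analysis a repeated-measures mixed model on log LDL-C at Visits 4 to 7, with treatment by visit, log baseline and centre, and take the between-arm contrast as the average of Visits 6 and 7. Monotherapy values then inform the model without standing in for combination values. State the estimand, and let it decide whether Visit 6 or 7 values obtained after discontinuation are included.

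Keep the LOCF and completer analyses as secondary. Probe the missing-at-random assumption with a delta-adjusted or similar missing-not-at-random sensitivity analysis. A retained LOCF run cannot do this, because it only substitutes a different assumption.

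For objective 7, name the set already defined in Section 6.3, patients with at least one on-combination value, as the main set, and never carry monotherapy values into the combination phase.

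The cost is wording and modest programming, with no new visits, samples or patients. The downside is reliance on missing-at-random.
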